Nurses at the primary care centers will get information about the study and the screening protocol from the data collector and project leader. There will be contact persons at each recruiting unit that will be responsible for the protocols and to contact the data collector when a patient fulfills all the criteria for participation. The project leader will have regular contact with the contact persons at the recruiting units. All screening protocols will be sent to the data collector. All participants will get orally and written information about the study from the data collector, and patients will provide written informed consent.

Randomization

Using a computer-generated list of random numbers, participants will be randomly assigned to being assessed, diagnosed and treated either by a physiotherapist or a physician first. A project coordinator is included among the health care providers in the study, but will not be involved in the screening procedure nor the data collection. The project coordinator will manage the sequence generation, allocation concealment, enrolment and assignments of participants and keep the concealed randomization scheme and sequentially numbered, sealed envelopes in a locked cupboard (in the same building where the enrolment will be), only available for the project coordinator. The project coordinator reveals the allocation to the participant shortly after the baseline measurement and to the health care providers.

Participants and health care providers in both groups will be aware of the allocated group, whereas data collector, data analyst and statistician will be kept blinded of allocation until completion of all outcome assessments.

The blinded data collector and analyst (is a physical therapist) whom is not involved in assessing diagnosing and treating patients with knee osteoarthritis while the study is conducted.

Data Collection

Measurements will be collected at baseline (before randomization), at 3-, 6-, and at 12 months follow up. All data will be coded and managed according to the Data Protection Act (1998:204), which means that all data will be confidential, and no unauthorized will have access to the patient registry. The results will be presented at group level; therefore, no individual information can be identified. Data will be saved for at least 10 years to enable audit.

Sample size

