To detect a minimal clinical improvement in health-related quality of life of 0.121(SD 0.2) on the EQ5D-index, with a two-sided 5% significance level and a power of 80%, a sample size of 50 patients per group will be necessary, given an anticipated dropout rate of 14%.

Statistical analysis

Data will be analyzed descriptively and presented as numbers and percent, mean and standard deviation or median and 25th to 75th percentiles. The primary outcome will be mean change in HrQoL (EQ5D-index and EQ5D-scale) and secondary outcomes will include mean change in pain intensity (VAS), physical performance (30CST) and self-efficacy (ASES-S). The changes in scores for the outcomes will be constructed by calculating raw differences between baseline and the follow ups.

For group comparison the X²-test will be used for nominal data and Fischer's exact test for small numbers, parametric student t-test for continuous variables and Mann-Whitney's test for ordinal data and at skewed distributions. Statistical analysis will be made in SPSS Windows and the analysis will be applied with intention-to-treat (ITT). The level of significance will be p< 0.05.

Study Design

Study Type: Interventional (Clinical Trial)

Actual Enrollment: 69 participants. Anticipated enrollment, 100 participants.

Allocation: Randomized

Intervention Model: Crossover Assignment

Masking: Double (Investigator, Outcomes Assessor)

Primary Purpose: Treatment

Arms and Interventions

Intervention: Physical therapy assessment

Patients allocated to the intervention group will be assigned to an assessment and evaluation by a physical therapist. If they are diagnosed with knee osteoarthritis they will get an offer to participate in a patient education program and physical training with an individualized exercise program made by a physical therapist. Patients will be offered individual treatment if they decline to participate in the education program, or if they have another diagnosis than osteoarthritis. Anytime after the first assessment by the physical therapist, the patient will be able to contact a physician if they want to.

Control: Physician assessment

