Allocation to the control group will involve an assessment and evaluation made by a physician. Further measures will then be determined by attending physician and the procedures that might get included are drug prescriptions, referral to x-ray examination, referral to a physical therapist or another health care provider. Anytime after the first assessment by the physician, the patient will be able to contact a physical therapist if they want to, even though if they have not been referred by the physician.

Outcome Measures

Primary Outcome Measures

Change from health related quality of life (HrQoL) at 12 months

[Time Frame: Baseline (before randomization) to 12 months]

A Swedish version of Euroqol-5 dimensions-3 levels (EQ5D-3L) will be used to assess perceived self-rated health-related quality of life. EQ5D-index respectively EQ5D-VAS will be presented. The questionnaire contain five dimensions and results in an index ranging from -0,549 to 1 using the UK tariffs. An index of 1 indicate full health. The EQ5D-VAS is a visual analogue scale ranging from 0 to 100, where 0 is worst imaginable health state and 100 is best imaginable health state.

Secondary Outcome Measures

Change from pain intensity at 12 months

[Time Frame: Baseline (before randomization) to 12 months]

The mean pain intensity (over the past month) will be measured by a visual analogue scale (VAS) ranged from 0 which will correspond no pain and 100 the worst imagined pain.

Change from physical function at 12 months

[Time Frame: Baseline (before randomization) to 12 months]

Physical performance will be measured with 30 seconds chair stand test (30CST). Number of stands will be counted.

Change from self-efficacy at 12 months

[Time Frame: Baseline (before randomization) to 12 months]

Self-efficacy will be assessed with Arthritis Self-Efficacy Scale-Swedish version (ASES-S). Each question range from 10-100, where 10 is very insecure and 100 is very confident. The questionnaire consists three subscales in how patients are experiencing their 1) pain, 2) physical function, 3) other symptoms. Each subscale results in a mean score ranging from 10 to 100 where 10 means very insecure and 100 means very confident.

Other Outcome Measures:

Demographic data

[Time Frame: Baseline (before randomization)]

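### Does the crossover label in the Study Design list conflict with the planned two-group analysis?

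*Combined protocol and SAP*

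**What the plan says.** The Study Design list has the entry "Intervention Model: Crossover Assignment".

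The operative sections describe something else:

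- **Randomization:** "participants will be randomly assigned to being assessed, diagnosed and treated either by a physiotherapist or a physician first". This is one allocation; no order of treatments is assigned.
- **Arms and Interventions:** there are two separate arms. For one, "Patients allocated to the intervention group will be assigned to an assessment and evaluation by a physical therapist"; for the other, "Allocation to the control group will involve an assessment and evaluation made by a physician".
- **Access to the other profession:** it is open in both arms. In the physical therapist arm, "Anytime after the first assessment by the physical therapist, the patient will be able to contact a physician if they want to"; in the physician arm, "Anytime after the first assessment by the physician, the patient will be able to contact a physical therapist if they want to". The physician may also refer to a physical therapist.
- **Data Collection and Outcome Measures:** there is one baseline before randomisation, with visits at 3, 6 and 12 months. The primary outcome is the change from that baseline to 12 months.
- **Sample size:** it is stated per group and is built on a "minimal clinical improvement in health-related quality of life of 0.121(SD 0.2) on the EQ5D-index".
- **Statistical analysis:** group comparisons use chi-square or Fisher's exact tests, a "parametric student t-test for continuous variables", and Mann-Whitney for ordinal or skewed data, under intention to treat.

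**The concern.** In a crossover trial each patient receives both treatments in randomised order, outcomes are recorded in each period, and the treatment effect is estimated within patients. The design model therefore decides which standard error is right. If this were a crossover, independent-groups tests would ignore the pairing, and the plan would be missing its treatment of period effects, carryover and washout. If it is a parallel trial, the declared model is wrong, and someone relying on that field, for example when extracting data for a meta-analysis, could give the result the wrong variance.

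The free access to the other profession adds to the unease. It could be taken as the reason for the label, and so raise doubt about whether data collected after such contact stay with the allocated arm.

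**Working it through.** **1. Reproduce the stated sample size as a parallel trial.**

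Inputs, all from the Sample size section: difference 0.121, SD 0.2, two-sided 5% level (z = 1.96), 80% power (z = 0.8416), dropout 14%. Equal allocation is implied by the equal group sizes.

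- Standardised difference: 0.121/0.2 = 0.605
- n per group = 2 × (1.96 + 0.8416)² / 0.605² = 42.9, rounded up to 43
- Allowing for dropout: 43/(1 − 0.14) = 43/0.86 = 50 per group, 100 in total

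This equals the stated 50 per group and the anticipated enrolment of 100. Power with 43 per group is 80.1% by the normal approximation and 79.2% by the t distribution. Sizing by the t-test instead gives 44 evaluable and 52 randomised per group, so the authors appear to have used the normal approximation for two independent means.

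**2. Could the same figure come from a crossover?**

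Take 0.2 as the SD of a single measurement and let ρ be the within-patient correlation. The document gives no value for ρ, so a range is assumed. For a two-period crossover:

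total N = 2 × (1 − ρ) × (1.96 + 0.8416)² / 0.605² = 42.9 × (1 − ρ)

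| Assumed ρ | Evaluable, total | After 14% dropout, total |
|---|---|---|
| 0 | 43 | 50 |
| 0.3 | 31 | 37 |
| 0.5 | 22 | 26 |
| 0.7 | 13 | 16 |

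No row approaches 100. At ρ = 0 the crossover total happens to be 50, but the plan states 50 for each group and anticipates 100 patients.

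**3. Look for the parts a crossover needs.**

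- Randomised sequence: absent; one allocation to a first assessor.
- Second period with its own baseline: absent; one baseline and one interval to 12 months for the primary outcome.
- Scheduled switch: absent; contact with the other profession is optional and has no fixed time.
- Washout, carryover or period terms: absent.
- Paired test: absent; all named tests compare independent groups.

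The eligibility criteria exclude anyone whose current knee pain has already been assessed by a healthcare provider. After a first period every patient would be in that state, so a first assessment could not be repeated in a second.

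**4. Effect of correcting the label.**

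Sample size: 50 per group before and after. Tests, endpoint, analysis set and estimate: unchanged.

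**The case for a change.** The strongest case for acting is that this field sits in the combined protocol and SAP, which readers use to learn how the effect and its standard error are obtained, and that one entry contradicts every other part. Correcting it costs almost nothing. The plan also never says in so many words what happens to patients who see the other profession, although both arms allow it freely.

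The contradiction stands. The consequences drawn from it are weaker:

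- Intention to treat does not rule out a crossover; crossover trials can be analysed by randomised sequence. The conflict is with the single allocation, the two separate groups and the independent-samples tests.
- Patient-initiated contact does not open a second treatment period. Crossover periods are set by protocol.
- A contrast such as 86 evaluable patients (parallel) against about 24 (paired t-test) assumes an SD of the within-patient difference of 0.2, equivalent to a correlation of 0.5 if the two periods have equal variance. It is one point in a wide range and measures no harm, since nobody sized this trial as a crossover.
- A sentence keeping patients in their allocated group would restate what intention to treat ordinarily means. The Brief Summary frames the question as the effect of a clinical pathway, and access to the other profession is written into both pathways.

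To mis-pool the result, a reader would have to overlook the per-group sample size, the named control group and the between-group tests.

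**Conclusion.** The label is a clerical slip in a registry-style list. The randomisation, arms, follow-up, sample size and tests agree with one another and describe a two-arm parallel trial; the planned 50 per group reproduces exactly on that basis. The entry should be read as parallel assignment, and a trial report would naturally describe it so. The effect on sample size, choice of test, estimate and conclusion is nil.

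The lack of an explicit rule for patients who contact the other profession is a gap that analysts fill sensibly from the stated intention-to-treat principle: they stay in the allocated group to 12 months, and the estimate compares the two pathways with that access included.

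This rests on two things: the usual meaning of intention to treat, and, for the crossover contrast only, an assumed within-patient correlation of 0 to 0.7. The conclusion does not depend on where in that range the correlation lies.

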STUDY PROTOCOL WITH STATISTICAL ANALYSIS PLAN

Official title:

Physical Therapist as Primary Assessor for Patients With Knee Pain in Primary Care

NCT number: NCT03715764

The Regional Ethical Review Board in Gothenburg approved the study 2013-03-15, reference numbers: 979–12, T674–13, T497–14, T791–15.

Document date: Protocol published and released on clinicaltrial.gov 2018-10-22.

Study Description

Brief Summary:

In order to manage the future increase in osteoarthritis consultation, patients with osteoarthritis could be assessed by a physical therapist first, so that other patients with more severe conditions could get faster access to a primary care physician. In Swedish primary care, physicians and physical therapists are primary assessors for patients with suspected knee osteoarthritis. However, it is unclear if there are any differences between these managements in improving health-related quality of life (HrQoL), pain, physical function and self-efficacy.

There is a limited amount of studies about the impact on HrQoL, pain intensity, self-efficacy and physical performance in patients with knee pain being assessed and evaluated by a physical therapist as a primary assessor.

The overall purpose of this study is to evaluate the effects on self-rated HrQoL, pain intensity, self-efficacy and physical performance with either a physical therapist or a physician as primary assessor for patients with knee pain within primary health care.

Problem statements

Which effect does a clinical pathway with a physical therapist as primary assessor for patients with knee pain...

... have on self-rated HrQoL compared with a physician as primary assessor?

... have on self-rated pain intensity compared with a physician as primary assessor?

... have on physical performance compared with a physician as primary assessor?

... have on self-efficacy compared with a physician as primary assessor?

It is expected that this study will show the effects of two different primary assessors for patients with knee pain consulting primary health care. The results could clarify which profession that is most appropriate to be the primary assessor for patients with knee pain in primary health care.

Detailed Description:

Patient Recruitment Recruiters: Primary care centers.

Screening procedure

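### Must the plan count physician visits before it can compare therapist-first with physician-first assessment?

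*Combined protocol and SAP*

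**What the plan says.** The Brief Summary opens with the expected rise in osteoarthritis consultations and suggests that a physical therapist could see these patients first, "so that other patients with more severe conditions could get faster access to a primary care physician". It then notes that both professions already act as primary assessors in Swedish primary care. The uncertainty it names is whether the two approaches differ in quality of life, pain, function and self-efficacy. The purpose statement and the four problem statements are confined to those domains. The section closes with one wider sentence: "The results could clarify which profession that is most appropriate to be the primary assessor".

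Under Randomization, "participants will be randomly assigned to being assessed, diagnosed and treated either by a physiotherapist or a physician first". Under Arms and Interventions, each arm may later reach the other profession. For the therapist-first arm, "Anytime after the first assessment by the physical therapist, the patient will be able to contact a physician if they want to". For the control arm, "Anytime after the first assessment by the physician, the patient will be able to contact a physical therapist if they want to", and the physician's own options include "referral to a physical therapist or another health care provider".

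Statistical analysis and Outcome Measures list EQ5D-index and EQ5D-VAS (primary), pain VAS, the 30-second chair stand test and ASES-S (secondary), and baseline demographic data with BMI (other). Visits, referrals and waiting times are not listed. The analysis is by intention to treat.

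**The concern.** A pathway meant to spare physician time does so only if its patients do not go on to see a physician anyway. The plan leaves that route open after the first therapist assessment and does not record how often it is used. If quality of life turned out similar in the two arms, the case for therapist-first assessment would rest largely on physician time saved. The same quality-of-life result would then read differently if one in ten therapist-first patients later saw a physician than if seven in ten did. The closing sentence of the Brief Summary, about which profession is most appropriate, seems to promise an answer that the planned data cannot fully give.

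Physician contact is also an outcome of the randomised pathways. It could be tabulated by arm as randomised without disturbing the main comparison, which makes its absence look like an easy omission to repair.

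**Working it through.** **1. Do the outcomes answer the stated questions?** Brief Summary set against Outcome Measures:

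| Problem statement | Measure |
|---|---|
| Quality of life | EQ5D-index, EQ5D-VAS |
| Pain intensity | Pain VAS |
| Physical performance | 30-second chair stand test |
| Self-efficacy | ASES-S |

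Every question has its measure. Physician access is neither a problem statement nor part of the stated purpose.

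**2. Does later contact bias the comparison?** Randomization assigns who assesses the patient first. Arms and Interventions then describes contact with the other profession as a permitted part of both pathways. An intention-to-treat comparison therefore estimates the difference between the two pathways as they would run in practice. No correction for later contact is needed.

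**3. Is the sample size affected?** Inputs from Sample size: difference 0.121, SD 0.2, two-sided 5%, power 80%, dropout 14%.

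- Per group: 2 × (1.96 + 0.8416)² × (0.2/0.121)² = 42.9, so 43.
- With dropout: 43/0.86 = 50 per group, as stated.

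This is the formula for two parallel groups. The crossover label under Study Design does not fit it, nor a single randomisation with 12 months of follow-up and no planned switch. The label is a clerical slip that alters no figure or test.

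**4. How much could an uncounted visit matter?** The documents give no contact rate, so every rate here is an assumption. Let p be the share of therapist-first patients with at least one knee-related physician visit, and assume every control attends the allocated physician assessment. Physician assessments avoided per 100 patients are 100 × (1 − p). Take 34 patients in the arm (69 enrolled, near-equal split assumed) and Wilson 95% intervals:

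(p + z²/2n ± z√[p(1−p)/n + z²/4n²]) / (1 + z²/n), with z = 1.96 and n = 34.

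| Assumed count | p, % (95% interval) | Avoided per 100 (95% interval) |
|---|---|---|
| 3/34 | 8.8 (3.0–23.0) | 91 (77–97) |
| 10/34 | 29.4 (16.8–46.2) | 71 (54–83) |
| 17/34 | 50.0 (34.1–65.9) | 50 (34–66) |
| 24/34 | 70.6 (53.8–83.2) | 29 (17–46) |

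In the other direction, if a share q of controls reach a physical therapist, the pathway adds 100 × (1 − q) therapist assessments per 100. That is 70 for q = 0.3 and 10 for q = 0.9.

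A visit count could thus separate a large saving from a small one even with 69 patients. The table says nothing about which saving is likely, because each row follows from its assumed p. It also counts patients with any visit and ignores repeat visits in either arm.

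**5. Would a visit count measure the stated rationale?** The rationale is quicker access for other, more severely ill patients. That would need waiting times or capacity at the centres. Visits by trial patients are one necessary link, not the quantity itself.

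**The case for a change.** The best case for acting is that the remedy looks cheap. One descriptive table of knee-related visits by arm could be drawn from unit records, or the closing sentence could be limited to the four measured domains. Neither touches the sample size, the primary test or patient care. A hedge in the wording does not supply the missing data, and readers may use that sentence to choose a pathway.

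Part of this stands. The trial cannot show whether therapist-first assessment reduces physician use, and any report that claims it does would go beyond the data.

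The rest is weaker. Enrolment is already reported as 69, so a visit table would be added after the fact. It would mean judging which visits were knee-related in records at several primary care centres, with consent and ethics cover to be confirmed; the documents mention no access to such records. Extraction would also have to wait, since "data collector, data analyst and statistician will be kept blinded of allocation until completion of all outcome assessments". Visits elsewhere would be missed. For the share with any physician visit, with controls fixed at 100%, this makes the saving an upper limit. For visit counts compared between arms, the error could go either way. Rewording the closing sentence would alter no analysis or result: it is tentative, carries no decision rule, and follows a sentence that speaks only of the effects of the two assessors.

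**Conclusion.** No change to the plan follows. The plan asks four questions and measures all four. The intention-to-treat comparison of the pathways is sound with later contact included, and the planned 50 per group reproduces. Physician access is background motivation, and a visit count would be an additional outcome that only partly reflects it.

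The size of the unmeasured effect is unknown. The span of 91 to 29 assessments avoided per 100 rests wholly on assumed contact rates, full attendance in the control arm and a near-equal split of the 69 patients. The limit concerns how the results are read: they can support statements on quality of life, pain, physical performance and self-efficacy, and none on physician workload or access. If record access is already covered, visits by arm could be reported as a descriptive extra, but the planned conclusions on the four outcomes do not depend on it.
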